## 1.0 Objectives / Specific Aims

The specific aims of this protocol are to:

**Aim 1.** (Months 03-12). To theater test and deliver the un-adapted CPT protocol and one session adherence intervention (Lifesteps) with 12 trauma-exposed PLWH presenting for HIV treatment at the MUSC Ryan White Clinic and collect qualitative feedback for modifications to ensure feasible administration and relevant incorporation of HIV-related messages and/or content specific to HIV-related PTSD. Specific activities are to:

- A. Test methods and measurement protocol of the beta version of the research protocol.
- B. Utilize feedback provided through exit interviews, topical experts, and advisory panel discussion to shape any refinement of the integrated CPT and one session adherence protocol.
- C. Incorporate qualitative feedback into the CPT-L manual.

**Aim 2.** (Months 13-30). To assess feasibility of the modified CPT protocol (CPT-L) compared to Lifesteps in 60 PLWH with comorbid PTSD over 3 months (baseline, post intervention, 3 month follow-up) in a pilot RCT to assess key variables for subsequent efficacy testing (attendance, ART adherence, HIV symptom distress, CD4 count, viral load, PTSD symptoms, avoidant coping). Specific feasibility benchmarks are:

- A. Achieve a recruitment rate of 4+ patients per month and retention rate of 80% or higher.
- B. Obtain variability estimates of outcomes (less than 10% missing data) and initial indicators of treatment effects for the following hypotheses in the subsequent efficacy trial:
  - a. Participants who receive the CPT-L protocol will have improved HIV symptom distress, ART adherence, clinic attendance, and viral load at post intervention and 3-month follow up vs. control.
  - b. Participants who receive the CPT-L protocol will report lower PTSD at post intervention and 3-month follow up versus those in the Lifesteps Control.
- C. Assess qualitative feedback from exit interviews for high satisfaction, successful saturation of themes, and action plan development, in conjunction with Advisory Board, to refine the intervention for an R01.

**Exploratory Aims.** 1) We will assess between-group differences in other problems that commonly occur among PLWH and PTSD (substance misuse, depression). 2) Avoidant coping will be examined as a potential mechanism of action for the relationship between CPT-L and improved adherence.

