
### 3.0 Intervention to be studied

Overview of Methods using the ADAPT-ITT framework. The proposed adaptation and pilot RCT follows a 2 (treatment type) × 3 (time points) at the MUSC Ryan White Clinic, ideally situated in the Southeast (i.e., a geographic jurisdiction identified in Phase 1 of EHE; where new HIV contraction rates remain in the top 10 in the US). The ADAPT-ITT model provides a framework for adapting HIV-related evidence-based interventions that is widely used in treatment studies with diverse populations. ADAPT-ITT consists of eight phases: (1) Assessment of needs of the target population, (2) Decisions around which empirically supported intervention to use or adapt, (3) Administration of novel methods (e.g., theater testing) to adapt the chosen intervention, (4) Production of a first draft of the adapted intervention, (5) Identification of topical experts, (6) Integration of content provided by topical experts for the second draft of the adapted intervention (7) Training staff to implement the adapted intervention, and (8) Testing the adapted intervention. This model has been successfully applied to the cultural adaptation of several HIV programs, including the PI's adaptation of an HIV prevention program for Latina adolescents (Davidson et al, 2014), and provides an empirically supported framework to understand the needs of individuals with comorbid PTSD and HIV and identify the “cultural” components (e.g., [[HIV-related intersectional stigma]], chronic disease coping, medication adherence, disclosure stress) that may not be addressed by evidence-based PTSD models. This team has begun initial steps of the ADAPT-ITT framework to determine whether adoption of or adaptation to evidence-based treatment was necessary to address this critical gap in comorbid PTSD and PLWH. PI [name] and colleagues highlight the need to modify CPT to fully encompass unique needs in the intersectionality of trauma and HIV status.

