In Aim 2, steps 7-8 of ADAPT-ITT will be completed. The project therapist is trained in evidence-based PTSD treatment, including CPT, thus Training in the integrated CPT-L protocol (step 7) will be relevant for adherence and stigma adaptations. For Testing the adapted intervention (step 8), we will randomize **60 adults** aged 18+ who meet DSM 5 criteria for PTSD and present for treatment at MUSC, Roper Ryan White Clinic, or other HIV care clinic, to either CPT-L + standard of care (SOC) or Lifesteps only + SOC. Participants must have experienced at least one traumatic event and report current clinically significant PTSD symptoms (via CAPS clinical interview). Participants randomized to experimental condition (CPT-L; N=30) will be assigned to the project therapist (trained and supervised in CPT-L). Participants randomized to control condition will receive the unadapted Lifesteps session as well as SOC (measured via chart review), which includes supportive services typically received by PLWH identified as suffering from PTSD. Assessments will be conducted at pre- and post-treatment, and 3-month post study-entry. Outcomes for efficacy testing in the subsequent R01 will be collected, including viral load, ART adherence, clinic attendance, PTSD diagnosis and symptoms, avoidant coping, substance use, and depression.

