**Assessments and Data Collection Procedures.** The PC (blind to condition) will conduct the initial eligibility (baseline) diagnostic assessments and all study assessments. The CAPS will be audio-taped and study personnel will listen to a randomly selected 20% to ensure reliability of CAPS diagnosis over the course of the study. The PC will administer the battery in the HIV care clinic or remotely by phone to the participant, based on participant preference. All timepoints will be collected on all participants, even if they drop out of treatment. Pilot trials indicate that major assessments take between 1.5 – 2 hours to complete. Individuals will be given \$50 for completing the baseline interview, \$40 for attending the first session, then \$60 for post-intervention assessments and 20-minute exit interview after completion of CPT-L sessions (i.e., post intervention ~6 weeks after study enrollment); and a \$75 gift card for 3 month follow up surveys. Several questionnaires were drawn from the PROMIS common data elements and NIH sponsored repositories to promote data sharing (e.g., PROMIS depression and BRICS Social Determinants of Health). Participants will complete a brief electronic diary on a weekly basis to assess use of resources/additional supports. Research has demonstrated the validity of this approach, including capturing “real-time” data beyond what can be captured with retrospective reports. Surveys (<1 minute each) will be electronically collected once a week for the 6 weeks of the intervention period starting one week after randomization (i.e., 6 electronic survey entries), leading up to the 3-month follow up. With input from the CAB, we have established procedures to auto-send an email or SMS text (participant choice) on a set schedule. SMS text messaging is possible via Twilio, embedded within our REDCap system, which allows participants to complete a survey directly from their phone, without having to access a webpage. Participants will be asked permission for the study team to access electronic medical records to collect CD4 count and viral load at the time of enrollment. As an attending physician in the clinic, Co-I [name] is familiar with these electronic records and will oversee the data pull. CD4 T-cell counts and HIV viral load will be measured as standard clinical practice using standard clinical assays (HIV viral load less than 200 considered virologic suppression). Relevant data from the clinic’s electronic medical record (e.g., CD4 count, no-shows) will be collected at intervals and study completion (i.e., 6 months after participation) to document retention in HIV clinical care using the industry standard of 2 appointments with a provider with prescribing privileges per year, no longer than 6 months apart. PI [name] has planned for adequate staff training and coverage based on experience. The PI will assist in training research staff on consent, diagnostic interview, assessment measures, and medical chart data retrieval (with Co-I [name] and Co-I [name] for service utilization data) and will conduct weekly meetings, quarterly reviews, and booster trainings to ensure standardized procedures. See Table 2 for research instruments.

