## 12.0 Data Management

### Sample size, Statistical Power and Analysis

Sample size justification. As the study is designed to demonstrate feasibility, sample size was determined based on pragmatic considerations, rather than formal power analysis. The study plans to enroll 60 PLWH randomized to CPT-L or Lifesteps. This sample size is adequate to assess feasibility outcomes (enrollment, attrition, retention, adherence to protocol and fidelity). The sample size recruited during our recruitment period (18 months) will allow the team to specifically justify that we can approach a reasonable sample for a larger RCT in an expanded recruitment period. Further, with a target retention rate of ≥90%, an enrolled sample of 60 participants produces a 95% confidence interval from 82% to 98% and an adherence rate of 80% will produce a 95% confidence interval between 70% and 90%. The study will produce both within and between treatment group estimates of visit attendance (yes/no), ART adherence (85% of doses taken), and proportion of detectable viral load (yes/no). Further, if mean HIV Symptom Severity, CD4 cell counts, PCL and CAPS-5 scores will be assessed post-intervention and a sample of 30 participants in each group will provide adequate power to determine estimated a confidence interval with a difference of ½ a standard deviation (0.51 SD) of the between group mean estimate. If the difference in proportion of participants with detectable viral load is 10% in the CPT group and 20% in the SOC Lifesteps group at the close of treatment (10% difference), the sample of 30 participants in each study group will provide an 18% confidence interval on either side of the estimated difference.

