
Data Analysis Aim 2. Descriptive analyses will characterize the entire sample and two conditions as appropriate using measures of central tendency or frequency distributions and proportions. Feasibility will be determined by patient willingness to be screened, proportion of participants meeting PTSD criteria, and flow of participants through the study. Feasibility of assessments will be examined through self-report and medical record abstraction. While CPT has been evaluated in other populations, acceptability within PLWH is important for feasibility data. Intervention feasibility will be monitored through randomization, session attendance and quality assurance data collection on intervention fidelity and supervision. Exit interviews will be analyzed using the same techniques for qualitative analyses described for Aim 1. Study feasibility will be determined by ability to adequately randomize and retain study participants throughout study intervention and follow-up, determined through ability to successfully randomize 4+ patients per month and retain 90% of randomized patients throughout the study. In addition to retention, a low rate of missing primary outcome data ( $\leq 10\%$  missing) will demonstrate ability to integrate the intervention with standard clinical care components and medical health records. Protocol adherence will be monitored weekly and reported as the proportion of weekly PCL checklists completed, and distribution of clinician rated treatment engagement and cooperation levels. Acceptable protocol adherence will be determined by completion of  $\geq 80\%$  of assigned weekly PCL checklists across participants.

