symptom severity more so in the CPT-L group compared to Lifesteps at the follow up clinic visit. Treatment group differences will be assessed using generalized linear models adjusted for baseline cell counts/symptom scores. Normality of model residuals will be assessed using Q-Q plots and data transformations will be performed as needed. The CAPS-5 and PCL will examine PTSD severity at baseline, post-intervention and 3-month follow-up. The PCL will be assessed weekly during study intervention and follow-up. Rates of change from baseline to post-intervention and follow up will be estimated with generalized linear mixed effects regression models. Linear slope trends over time and associated standard errors will be calculated for each treatment assignment using a single model for all data. Estimated CAPS, PCL, and HIV symptom severity scores and associated standard error estimates will be calculated for each study group at each study visit and effect size estimates (Cohen's  $d$ , partial eta) will be tabulated and reported. As PCL scores are measured weekly, non-linear mixed effects models will be fit to not any cubic or quadratic trends that occur during study treatment and estimates of when treatment efficacy begins to show changes in effect size will be assessed and reported.

Exploratory investigations of substance use/misuse will be collected using the AUDIT and DAST. Changes in the proportion of participants reporting substance use between groups following study treatment and follow-up will be compared using modified Poisson regression models adjusted for baseline use and study treatment. Continuous AUDIT and DAST scores will be assessed in those who report use and compared between groups using generalized linear mixed effects models. Depression will be assessed at the same time points using the PROMIS Emotional Distress-Depression short form. Both raw and prorated T-scores will be assessed at each timepoint and treatment group comparisons will be made using generalized linear mixed effect models, adjusted for baseline PROMIS scores and study visit. Exploratory models will be adjusted variables used to balance the randomization procedure and those correlated with study outcomes. Secondary analysis of additional measures (QOL, HIV Stigma, Intersectional Stigma, ERQ) will be assessed between study groups using appropriate statistical methods. Analyses will be conducted using SAS version 9.4 (SAS Institute, Cary, NC, USA).

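### The CD4, HIV symptom, CAPS and PCL models do not list the urn factors; two smaller points, the AUDIT/DAST user subset and the model behind the visit-specific CAPS estimates, also need stating (low priority)

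*Combined protocol and SAP*

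**What the plan says.** Section 12.0 (Data Analysis Aim 2) sets out its models family by family:

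- **Binary outcomes** (attendance, ART adherence, detectable viral load): treatment, visit, their interaction, and the balancing variables.
- **Exploratory outcomes** (substance use, depression): the balancing variables are again included.
- **CD4 count and HIV symptom severity**: generalized linear models adjusted for the baseline value. No other covariate is listed.
- **CAPS and PCL**: mixed models for rates of change, with no covariates listed. "Linear slope trends over time and associated standard errors will be calculated for each treatment assignment using a single model for all data." The next sentence promises that "Estimated CAPS, PCL, and HIV symptom severity scores and associated standard error estimates will be calculated for each study group at each study visit", with Cohen's d and partial eta-squared, but names no model. Quadratic and cubic terms are planned for the weekly PCL only.
- **AUDIT and DAST scores**: compared between arms among participants who report use. When use is determined is not stated.

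Section 10.0 (Randomization Procedures) names viral load and self-identified gender as the urn factors. Shortly afterwards it says that the baseline assessment precedes randomisation so that symptom severity is available for the urn.

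Hypothesis b in section 1.0 is about two visits: "Participants who receive the CPT-L protocol will report lower PTSD at post intervention and 3-month follow up versus those in the Lifesteps Control". Section 10.0 places them at "post intervention ~6 weeks after study enrollment" and, for follow-up, states: "Assessments will be conducted at pre- and post-treatment, and 3-month post study-entry".

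**The concern.** Factors that restrict the allocation normally belong in the analysis model. The plan follows this for two families of outcomes and is silent for the continuous HIV and PTSD outcomes, and no general sentence extends the rule to them. Leaving the factors out of a linear model causes no bias, but the reported intervals are a little wider than they need be. The covariate list cannot be finalised while section 10.0 leaves the status of symptom severity open.

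The AUDIT/DAST subset raises a different issue. The same paragraph compares the proportion reporting use between arms after treatment, so the plan itself treats use as something the intervention may change. If the score comparison is restricted to participants who report use after randomisation, the two subsets are no longer comparable by design.

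For CAPS, two analysts could follow the text faithfully and report different post-intervention effect sizes, one from a fitted line and one from visit means. These estimates are meant to aid development of the later R01.

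**Working it through.** **1. The plan's own precision figure.** With 30 per arm, the 95% half-width for a mean difference is 1.96 × √(2/30) = 0.506 SD. The plan states 0.51 SD, so it reproduces.

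**2. Urn factors.** Take outcome SD 1, baseline–outcome correlation ρ, and factors that explain a share R² of the variance at both times. No document gives ρ or R²; both are assumed.

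- Residual variance with baseline only: 1 − ρ².
- Residual variance with baseline and factors: (1 − R²) − (ρ − R²)²/(1 − R²).
- Ratio of standard errors, without to with the factors: the square root of the first over the second.

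| ρ | Baseline only | With factors, R² = 0.1 / 0.2 / 0.3 | SE ratio |
|---|---|---|---|
| 0.5 | 0.750 | 0.722 / 0.688 / 0.643 | 1.019 / 1.044 / 1.080 |
| 0.7 | 0.510 | 0.500 / 0.488 / 0.471 | 1.010 / 1.023 / 1.040 |

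A simulation agrees closely. It used 6,000 trials per setting, N = 60, 26% not male (25% + 1% from section 5.0) and an assumed 40% with detectable viral load. Ratios for R² = 0.1 / 0.2 / 0.3:

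- Allocation balanced within strata: 1.017 / 1.043 / 1.077 (ρ = 0.5) and 1.008 / 1.021 / 1.038 (ρ = 0.7).
- Complete randomisation: 1.001 / 1.026 / 1.061 and 0.992 / 1.006 / 1.021. At the low end the gain vanishes.

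**3. AUDIT/DAST.** No arithmetic is possible, because the plan gives no expected proportion of users. The subset is harmless if use is fixed at baseline and is affected by treatment if use is taken later. The text fits either.

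**4. CAPS, if the visit values were read from the line.** Let d be the true arm difference at week 6, and assume it is kept to month 3 (week 13). The differences at weeks 0, 6, 13 are then (0, d, d).

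- Mean time 6.333; sum of squares of time 84.667; cross-product 6.333d; slope 0.0748d per week; mean difference 0.667d.
- Fitted at week 6: 0.667d − 0.333 × 0.0748d = 0.64d.
- Fitted at week 13: 0.667d + 6.667 × 0.0748d = 1.17d.
- If month 3 is week 12: 0.67d and 1.17d. If week 14: 0.62d and 1.16d.
- With a common baseline for the arms: 0.48–0.56d and 1.03–1.21d.
- If half the gain is lost by follow-up: 0.49d at week 6. If the difference grows linearly: 1.00d, no bias.

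At an assumed d = 0.5 SD, the plateau shifts the post-intervention estimate by 0.5 × (0.642 − 1) = −0.18 SD, about a third of the plan's 0.51 SD half-width.

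The PCL is partly protected. Under the same plateau a straight line through the weekly scores gives 0.70–0.71d at post-intervention, the quadratic 0.89–0.93d and the cubic 0.90–0.99d.

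**The case against.** Much of the opposing case stands.

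- **Silence is not omission.** A reader might infer that the plan means to leave the urn factors out of the continuous models. It does not say so. The moderator analyses in section 12.0 would also add terms for sex and gender identity and for history of viral suppression, which lie close to the urn factors. Those are separate exploratory models, however, and history of suppression is not the same variable as viral load in the urn. The main models remain unspecified.
- **A visit-based reading of CAPS is available.** A reader might infer that the CAPS effect sizes will be read from the fitted line and so be biased. The documents do not show this. Section 3.0 says "The proposed adaptation and pilot RCT follows a 2 (treatment type) × 3 (time points", which describes a factorial layout. The sample-size text says "PCL and CAPS-5 scores will be assessed post-intervention and a sample of 30 participants in each group", a single-visit contrast. The mixed model for rates of change to post-intervention and to follow-up can be read as two separate changes. The sentence promising visit-specific scores also covers HIV symptom severity, which has a different model, so it cannot refer to the line alone.
- **A categorical-visit model is not better in every respect.** Without baseline adjustment its post-intervention standard error is √(2/30) = 0.258 SD. At an assumed d = 0.3 with a plateau, the unadjusted line's root mean squared error is 0.217 / 0.237 / 0.255 at within-person correlation 0.3 / 0.5 / 0.7, lower each time. The case for categorical visit is that it answers the stated hypothesis without assuming a shape, not that it always has the smaller error.
- **Low stakes.** "Study feasibility will be determined by ability to adequately randomize and retain study participants" sets the terms on which this pilot is judged.

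**Conclusion.** The point holds as a set of specification gaps of low priority. The firmest is the covariate list: the balancing variables appear in the binary and exploratory models but not in the CD4, HIV symptom, CAPS and PCL models. Adding them brings a small precision gain and no change in bias. The standard error without them is roughly 1–8% larger, given an assumed R² of 0.1–0.3, correlation of 0.5–0.7 and near-balanced allocation.

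The AUDIT/DAST comparison is a fault only if use is taken after randomisation, which the text leaves open.

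The CAPS item is a request to name a model, not a demonstrated error. The figures of 0.64d and 1.17d need both a reading from the line and a plateau, and the documents establish neither.

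The plan also anticipates that treatment will lower CD4 counts, which does not fit its aim of improved HIV outcomes. That is a wording correction only. No decision rule depends on it or on any effect size discussed here.

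**What to change.** 1. Add the urn factors to the CD4, HIV symptom, CAPS and PCL models, in the form in which they enter the urn. Reconcile section 10.0 on whether symptom severity is also an urn factor.
2. Compare AUDIT and DAST scores in all randomised participants, or in users defined at baseline. The first may bring many zero scores; the second a smaller sample.
3. State that the post-intervention and 3-month CAPS differences and Cohen's d come from a mixed model with categorical visit, visit-by-arm interaction and baseline score. Keep the slopes as descriptive.
4. Correct the anticipated direction for CD4.

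The cost is SAP wording and a few lines of SAS, using data already planned for collection. The downside is a few more parameters at n = 60. The categorical model can also have the larger standard error when within-person correlation is low: at 0.3, with baseline adjustment, √((2/30) × (1 − 0.09)) = 0.246 SD, against 0.189 SD for a line without baseline adjustment. Its root mean squared error can likewise be larger when that correlation is low or the effect is small.

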symptoms, as well as traumatic stress, substance use, and depression among civilian and military adults with complex trauma histories. CPT reduces trauma-related self-blame and guilt, two factors intimately tied to avoidant coping. Most importantly, reductions in avoidance symptoms (in the context of traumatic stress symptoms) have been linked to increases in (non-HIV) medical regimen engagement, including medication adherence. Mental health treatment studies in adults with Type 2 diabetes (another chronic disease with self-management and adherence barriers) have demonstrated that interventions leading to mental health symptom reduction showed simultaneous improvements in medication adherence, HbA1C scores, and self-care behaviors. Although CPT has been enhanced to target alcohol use and high risk sexual behavior to prevent HIV among American Indian women, CPT, nor other gold-standard, empirically supported individual treatments (e.g., Prolonged Exposure/PE), have been adapted for PLWH or evaluated as an efficacious approach to reduce problematic HIV outcomes. Thus, there is critical need to examine evidence-based treatments for PTSD among PLWH and co-occurring PTSD to improve HIV outcomes. CPT may be particularly beneficial for PLWH due to the focus on unhelpful cognitions, or “stuck points,” in the form of assimilation (beliefs related to self-blame) and overaccommodation (extreme beliefs related to self and world). The flexibility of CPT to focus on unhelpful thoughts and thinking patterns would allow patients to address trauma- and HIV-related intersectional stigma cognitions in treatment. In line with the Undetectable=Untransmittable (U=U) initiative to end HIV-related stigma, this proposal has broad implications not only from a public health standpoint, but also for the self esteem of individuals by reducing HIV-related stigma [[and other intersecting stigmatized identities]]. Themes addressed in CPT (i.e., safety, intimacy, trust, esteem, power, and control), although originally created from theory on sexual assault, may have relevant overlap to unique issues in disclosing HIV status, and with managing and coping with HIV in interpersonal and intrapersonal domains. [[Given that 28-52% of PLWH are estimated to experience cognitive impairment (CI), CPT is particularly well-matched for application with this population, as CPT has been delivered successfully with veterans who have experienced traumatic brain injury (TBI), resulting in cognitive and affective symptoms similar to PLWH with CI.]] CPT dismantling studies have also demonstrated improved engagement and PTSD outcomes among complex and traditionally hard-to-reach populations, and can potentially decrease substance use in addition to PTSD symptoms, further supporting the intervention for complex mental health treatment needs of PLWH. Taken together, an empirically supported adaptation of CPT for PLWH (i.e., CPT-L) may improve HIV treatment outcomes for PLWH with comorbid PTSD. This study will address vital gaps by conducting the first pilot RCT to use an adapted evidence-based PTSD treatment, integrated with an evidence-based adherence session, (Lifesteps), to improve HIV outcomes among PLWH with co-occurring PTSD in a geographic jurisdiction identified in Phase 1 of the national End the Epidemic plan. To accomplish this goal, across 3 time-points, we will rigorously measure: trauma history, PTSD symptoms and diagnosis, viral load, CD4 count, stigma, ART adherence, clinic attendance, substance misuse, depression, and avoidant coping.

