Randomization Procedures. For Aim 2, we will use an adaptive randomization procedure (urn randomization) to balance confounding variables among participants in each condition. Factors on which the adaptive randomization procedure will operate are viral load and self-identified gender. Computerized urn randomization will use an adaptation of Microsoft Access application gRand (used by Co-I [name]). Efforts will be made to keep the project coordinator (PC) blind to condition, therefore, PI [name] will randomize participants. Participants will be randomized following consent and baseline assessment (to determine severity of symptoms for the urn) to one of two conditions: (1) CPT-L + Standard of Care (SOC) or (2) Lifesteps + SOC. Within 7 days of interview and PI's randomization, the PI will contact the participant to inform him/her of condition. Case managers will do phone check-ins between sessions to encourage attendance and provide referrals and information to individuals in both CPT-L and Lifesteps groups. Individuals in the Lifesteps condition will receive the one-session adherence intervention in addition to any other standard treatment that a PLWH with PTSD symptoms would typically receive at a HIV care clinic. SOC treatment will vary in type, duration, and frequency (e.g.,

spiritual counseling, crisis hotline phone call, resource help for case manager,), but will be measured carefully across both conditions through coding of chart review and weekly electronic dairy assessment of service utilization (methods used successfully by Co-I [name] in prior RCTs) to account for Treatment dosage. Baseline, post-intervention and follow-up assessments will be collected by the PC. In the CPT-L condition, the PI, assigned case manager, and project therapist will make contact within 7 days of randomization. Participants in the control condition will be contacted by one of the Lifesteps-trained HIV care case managers.

Figure 2. Participant Flow Diagram

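### AUDIT and DAST scores are compared between arms only among people reporting use, with no visit or score defining use; if users are taken at the analysed visit, the difference is not a randomised comparison

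*Combined protocol and SAP*

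**What the plan says.** Section 12.0, Data Analysis Aim 2, plans two analyses of substance use. The first covers everyone: "Changes in the proportion of participants reporting substance use between groups following study treatment and follow-up will be compared using modified Poisson regression", using "modified Poisson regression models adjusted for baseline use and study treatment". The second is restricted: "Continuous AUDIT and DAST scores will be assessed in those who report use and compared between groups using generalized linear mixed effects models". On covariates, the same paragraph adds: "Exploratory models will be adjusted variables used to balance the randomization procedure and those correlated with study outcomes".

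No section says at which visit, or from what score, a participant counts as reporting use. Table 2 schedules both scales at baseline, post-intervention and 3 months, so several definitions are possible.

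Three other places bear on the point. Section 2.0 says that CPT "can potentially decrease substance use in addition to PTSD symptoms". Section 1.0 lists between-group differences in substance misuse as an exploratory aim. Section 10.0 names, among the outcomes collected for the subsequent R01, "PTSD diagnosis and symptoms, avoidant coping, substance use, and depression".

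**The concern.** Three readings of the restriction are open:

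- **Users at the analysed visit.** Membership depends on something that happens after randomisation and that treatment may change. Participants who stop using under CPT-L leave the CPT-L side of the comparison. Adjusting for baseline score does not put them back.
- **Anyone reporting use at any assessment, with all scores kept.** The subset is still partly formed after randomisation, but people who stop stay in it.
- **Users at baseline.** Membership is fixed before allocation, so the comparison remains a randomised one.

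The first reading is a natural one. One sentence earlier the plan names baseline use when it means baseline, and it treats later use as an outcome. At stake is one exploratory score difference, which could look like no effect, or like harm, while use was in fact falling. Leaving the definition open also allows it to be chosen after the data are seen.

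**Working it through.** The documents give no use rate, score distribution or expected effect for AUDIT or DAST, so there is no plan figure to reproduce. All inputs below are assumptions.

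**Mechanism.** At one visit let p be the proportion scoring above 0 and m the mean score among them. The mean over everyone is p × m. With 1 for CPT-L and 0 for control:

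- all randomised: p1·m1 − p0·m0
- users at that visit: m1 − m0

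The second expression omits whatever works through p.

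**Inputs.** Latent scores are normal with SD 6, mean 2 or 4, and correlation between visits 0.5, 0.7 or 0.85. The score is the rounded latent value, with a floor of 0. Control users: P(latent > 0.5) = Φ(1.5/6) = 60% or Φ(3.5/6) = 72%. The CPT-L effect takes one of four patterns:

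- A: 25% of users stop, regardless of score
- B: half of those scoring 1 to 5 stop
- C: every latent score falls by 2 points
- D: 25% of those scoring 8 or more stop

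Two means and three correlations give 6 settings per pattern, 24 in all.

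**By hand (mean 2, one visit, no baseline adjustment).** The control mean over everyone is 3.523, so m0 = 3.523/0.5987 = 5.884.

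- A: m1 = m0, so the users-at-visit difference is 0. All randomised: −0.25 × 3.523 = −0.88.
- B: scores 1 to 5 are held by 31.9% of people and contribute 0.939 to the mean. All randomised: −0.5 × 0.939 = −0.47. p1 = 0.5987 − 0.1594 = 0.4393 and m1 = (3.523 − 0.470)/0.4393 = 6.950. Users at visit: 6.950 − 5.884 = +1.07.

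**With baseline adjustment.** A random-intercept model was fitted with arm, visit, arm by visit and baseline score, with 100,000 per arm and the arm effect averaged over both follow-ups. The urn factors were not simulated. Entries are CPT-L minus control in score points, as ranges over 6 settings:

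| Pattern | All randomised | Users at visit | Any-visit users | Baseline users |
|---|---|---|---|---|
| A | −0.88 to −1.25 | −0.03 to 0.00 | −0.92 to −1.48 | −1.20 to −1.65 |
| B | −0.47 to −0.49 | +0.50 to +0.96 | −0.35 to −0.61 | −0.51 to −0.63 |
| C | −1.12 to −1.39 | −0.91 to −1.46 | −1.26 to −1.67 | −1.43 to −1.73 |
| D | −0.47 to −0.81 | −0.17 to −0.42 | −0.59 to −0.98 | −0.73 to −1.11 |

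The columns have different denominators, so compare signs first. In B, adjustment brings +1.07 down to +0.50 to +0.96, which is smaller but not removed. Only the users-at-visit column ever has the wrong sign. Any-visit and baseline users keep the correct sign in all 24 settings.

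**At 30 per arm (1,000 trials, A and B only).** The 95% half-width is 1.47 to 1.99 points for users at visit and 1.10 to 1.82 for all randomised. The distortion therefore lies within sampling error. The estimate is above zero in 73–83% of trials in B (all randomised: 19–34%) and in 49–52% in A (all randomised: 6–14%).

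**Sensitivity.** If 10–30% of light scorers stop in B, and not 50%, the users-at-visit difference is +0.08 to +0.51. A second score shape was also tried: gamma among users, mean 8, SD 6, with 15% or 30% of users stopping, unadjusted. The users-at-visit difference was +1.1 or +2.4 if the lightest stop, about 0 if stopping is unrelated to severity, and −2.0 or −3.1 if the heaviest stop. Among baseline users the same data gave −0.2 or −0.7, −1.2 or −2.4, and −2.9 or −4.6.

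**The case against.** **The text does not establish a biased analysis.** It leaves a term undefined, and the any-visit and baseline readings kept the correct sign throughout. This stands, and the point is therefore conditional. It is still more than a missing detail, because the restriction is stated and one natural reading of it selects on an outcome.

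**The two analyses form a two-part description.** The proportion using is compared in everyone and would show stopping. A value near zero in pattern A is then the right answer to how severe use is among those who remain. This stands too. What remains is that the plan presents the second part as a comparison between groups.

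**The reach is short.** A reader might infer that a distorted substance use effect size passes into the R01. The documents do not support that much. The tabulated effect sizes in section 12.0 are for CAPS, PCL and HIV symptom severity. The sentence on parameter and variability estimates goes on to specify HIV outcomes. Aim 2's list of key variables omits substance use. The link rests only on the outcome list in section 10.0.

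**The inputs are assumed.** One score distribution stands for both scales. Stopping is taken to give a score of 0 at once, while the documents state no recall period. Reversal needs mainly lighter users to stop. A reader might infer that the trial is likely to report apparent harm, and nothing in the documents supports that.

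**Intention to treat.** A reader might also infer a breach of the statement in section 14.0. That statement concerns data from withdrawn participants and does not say who enters the score model.

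**Conclusion.** The point holds in a conditional form, and it is minor. The plan does not define who counts as reporting use. If users are taken at the analysed visit, the AUDIT or DAST difference describes severity among remaining users and is not a randomised comparison, even after baseline adjustment.

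Under the assumed inputs, that difference is near zero when stopping is unrelated to score, reversed when only lighter users stop, diluted when heavier users stop, and correct in sign under a uniform drop. The direction and size in this trial cannot be derived from the documents.

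The unrestricted comparison of the proportion using is unaffected, as are every feasibility benchmark and every HIV and PTSD outcome.

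**What to change.** Make the between-arm score analysis one of all randomised participants with available AUDIT or DAST scores, each entered at the scored value, zeros included. Adjust for baseline score, visit, treatment by visit and the urn factors ("Factors on which the adaptive randomization procedure will operate are viral load and self-identified gender"). Use robust standard errors or another method that tolerates many zeros.

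If a users-only comparison is kept, define users separately for each scale by a baseline score above 0 (AUDIT for alcohol, DAST for drugs). Keep all their follow-up scores, including zeros.

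Label any comparison among follow-up users as descriptive, to be read together with the proportion using.

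**Cost.** A few sentences in the analysis plan and no new data: Table 2 schedules both scales at all three assessments, and section 10.0 states: "All timepoints will be collected on all participants, even if they drop out of treatment". The downside of the all-randomised model is the number of zeros in a sample of 60. Under the assumed inputs these are 28% to 40% of the control arm (1 − 0.72 and 1 − 0.60), and more in CPT-L if people stop. The downside of a baseline-user subset is precision. If 30%, 50% or 70% use at baseline (assumed), 9, 15 or 21 per arm remain, and 1.96 × √(2/n) gives half-widths of 0.92, 0.72 or 0.61 SD before dropout, against 0.51 SD with all 30.
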